## 4.7.1.1. Immunogenicity Analyses

All immunogenicity analyses will be performed on the Immunogenicity Analysis Set.

Immunogenicity variables include antidrug antibody (ADA) status, ADA response category, and ADA or neutralizing antibody (NAb) incidence and titer over the duration of the study as follows.

The summaries of ADA incidence over the duration of the study will include the following response categories:

• **ADA negative:** An ADA-negative signal in the ADA assay at all timepoints collected for ADA analysis

• **ADA positive:** An ADA-positive signal in the ADA assay at any timepoint collected for ADA analysis

Participants who are ADA positive may be further categorized into ADA response categories as follows:

• **Pre-existing immunoreactivity:** An ADA-positive response with either of the following 2 conditions met:

- ADA-positive response at Baseline with all post-first dose ADA results negative

OR

- ADA-positive response at Baseline with all post-first dose ADA responses
   < 4-fold over the baseline titer level

- **Treatment-emergent ADA responses:** An ADA-positive response post-first dose when baseline results are negative or missing
- **Treatment-boosted ADA responses:** An ADA-positive response post-first dose that  $is \ge 4$ -fold over the baseline titer level when the baseline result is positive

Study participants with a treatment-emergent or treatment-boosted ADA responses may be further categorized as follows:

- **Persistent**: ADA responses with 2 or more consecutive ADA-positive samples separated by at least a 16-week period, with no ADA-negative samples in between, irrespective of missing samples
- Indeterminate: ADA-positive samples only at the last collected sample
- **Transient:** An ADA response that is neither a persistent nor an indeterminate response

ADA-positive samples will be further characterized for neutralizing activity in the NAb assay. NAb status categories are as follows:

- NAb positive
- NAb negative

Association of immunogenicity with impact on exposure, safety, and efficacy:

- Association of immunogenicity with an impact on exposure: Associations between ADA response categories or NAb and systemic exposure to ravulizumab may be explored to assess the potential impact of immunogenicity on drug concentration-time (PK) profiles.
- Association of immunogenicity with an impact on safety: Associations between ADA response categories or NAb and serious and severe AEs may be explored, including SAEs such as systemic hypersensitivity, anaphylaxis, injection/infusion site reactions lasting > 24 hours, and other immune-related SAEs.

• Association of immunogenicity with an impact on efficacy: Associations between ADA response categories or NAb and key efficacy endpoints or variables may be explored to assess the impact of immunogenicity on drug efficacy.

## 4.8. Subgroup Analyses

No subgroup analyses will be performed.

#### 4.9. Interim Analyses

An unblinded interim analysis may be conducted for futility when approximately 24 (67%) of all participants complete the Week 26 Visit or have discontinued prematurely. The comparative primary and safety data will be assessed at this interim analysis. There is no plan to alter Part A study design, and thus, no adjustment is needed for Type 1 error at the final analyses.

The unblinded interim analysis will be conducted by the IDMC. The IDMC SAP includes details of the interim analysis.

At the time of the interim analysis, there will also be additional analyses generated to support an Unblinded Review Committee (independent of the study team). The details of the Unblinded Review Committee are specified in a Unblinded Review Committee Charter document.

## 4.10. Changes to Protocol-Planned Analyses

Not applicable.

## 5. SAMPLE SIZE DETERMINATION

A total number of 36 participants will be randomized into the study with a 2:1 (ravulizumab:placebo) allocation ratio to ensure approximately 80% power to detect a difference (ravulizumab-placebo) of 45% in TIS40 response rates with a 2-sided Type 1 error of 0.2, assuming a placebo response rate of 23% and an approximately 20% dropout rate.

The sample size was calculated in PASS2022 using the 2-sample test for the difference of proportions with a pooled estimate of variance for the primary endpoint (TIS40).

## 6. SUPPORTING DOCUMENTATION

#### 6.1. Technical Specifications for Derived Variables

#### 6.1.1. Baseline Definitions

#### **Baseline Definitions Applied to the RCP:**

To calculate TIS, a Baseline must be defined for each of the 6 CSMs.

For 5 of the CSMs (excluding muscle enzymes), the Baseline of the CSM will be defined as the latest non-missing value prior to the first dose of study intervention (ravulizumab or placebo).

For the sixth CSMs (muscles enzymes, which consist of creatine kinase, aldolase, alanine aminotransferase, aspartate aminotransferase, and lactate dehydrogenase), the latest non-missing value prior to the first dose of study intervention will be selected. The Baseline of the most abnormal muscle enzyme will be the laboratory value of the enzyme with the highest ratio (result/ULN).

For other parameters, the Baseline will be defined as the latest nonmissing value prior to the first dose of study intervention (ravulizumab or placebo), unless otherwise specified.

For the placebo participants who later receive ravulizumab during the OLE Period, an additional Baseline will be summarized. The Baseline will be defined as above, but it will be relative to the first dose of ravulizumab.

#### 6.1.2. Visit Windows

For tables and figures, all summaries by timepoint during the RCP will be tabulated and analyzed per the scheduled visit as recorded on the electronic case reports forms (eCRF) even if the assessment is out of window. For shift table summaries, these will include unscheduled visits.

Unless otherwise specified, data collected at an unscheduled visit or Early Termination will be included in by-participant listing and/or spaghetti plots figures, but no assignment of the scheduled visit will be made for the purposes of tabulations. For the calculation of baseline, unscheduled visit will be considered. For shift tables, unscheduled visits or Early Terminations visits will be considered for worst post-baseline.

For the placebo participants who later receive ravulizumab during the OLE Period, an additional visit will be summarized. The Baseline will be remapped relative to ravulizumab (eg, Week 26 remapped to Day 1, and Week 28 relative to Week 2).

#### 6.1.3. Study Day

Study Day 1 will be the defined as the first date of study intervention (ravulizumab or placebo). Day is relative to the first dose date of the study intervention for all participants.

If the assessment is after the first dose date, the study day will be calculated as follows:

• Study day = date of assessment - date of the first dose of study intervention + 1

If the assessment is before the first dose date, the study day will be calculated as follows:

• Study day = date of assessment - date of the first dose of study intervention

For participants who were randomized to placebo but later received ravulizumab, the participant will have additional variables in listings. These variables will reflect the data closest to the first dose of ravulizumab.

- Baseline value: relative to the first dose of placebo and relative to the first dose of ravulizumab in OLE
- Study day: relative to the first randomized dose of placebo and relative to the first dose of ravulizumab
- Visit: based on actual study visit and visits remapped relative to the first dose of ravulizumab

#### 6.1.4. Derivation of TEAEs for Incomplete or Missing Date of Onset

If both start and end dates of AEs are completely missing, no imputation will be performed and those AEs will be considered treatment emergent.

If the start date is partial:

- 1. If only the day is missing:
  - a. If the month/year of the start date is the same as those of the first study intervention administration date, then the missing day will be imputed as the smaller nonmissing value of (day of the first study intervention administration, day of the AE end date).
  - b. Otherwise, impute the missing day as "01."
- 2. If both day and month are missing:
  - a. If the year of the AE start date coincides with the year of the first study intervention administration date, the partial start date will be set as the first study intervention date. If this leads to a date after the AE end date, then the missing day and month of the AE start date will be imputed as the day and month of the AE end date.
  - b. If the year of the AE start date is different from the year of the first study intervention administration date, the missing day and month of the AE start date will be imputed as "01" and "01."

If the stop date is partial:

- 1. If only the day is missing:
  - a. The missing day will be imputed as the last of the month, adjusting for the leap year.
- 2. If both day and month are missing:
  - a. If the year of the AE end date coincides with the maximum of (the year of the first study intervention administration date or the year of the last study intervention administration), then the missing month will be imputed as the month of the corresponding study intervention administration date (first or last) and the missing day will be imputed as the last of the month adjusting for the leap year.
  - b. Otherwise, the missing day and month of the AE stop date will be imputed as the "31" and "12."

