#### 4.6.2. Adverse Events

AEs will be classified using the Medical Dictionary for Regulatory Activities (MedDRA Version 26.0 or later) and displayed in tables using System Organ Class (SOC) and Preferred Terms (PT). Treatment-emergent AEs are defined as any AE with a start date on or after the first dose of study intervention in the RCP.

An AE overview table will be tabulated. This table will include the number and percentage of participant in the following categories such as, but not limited to, the following:

- At least 1 treatment-emergent adverse event (TEAE)
- At least 1 drug-related TEAE
- At least 1 TEAE of Grade 3, 4, or 5
- At least 1 serious TEAE
- At least 1 serious related TEAE
- At least 1 adverse event of special interest (AESI)
- At least 1 AE leading to treatment discontinuation
- At least 1 drug-related AE leading to treatment discontinuation
- At least 1 infusion-related reaction

Tabulations by SOC and PT displaying the number of participants (percentage) and total event will be generated for the following tables:

- All TEAEs
- TEAEs of Grade 3, 4, or 5
- AEs related to treatment
- AEs related to treatment by maximum severity
- AESI
- Serious Adverse Events (SAEs)
- SAEs related to treatment
- AEs leading to treatment discontinuation
- Infusion Associated Related Reactions

Separate listings will be provided for deaths, SAEs, and any AEs leading to study withdrawal or treatment discontinuation. In addition, a separate AE listing will be generated for any AE related to COVID-19.

In addition, there will be a separate listing for any pretreatment AEs. These AEs will not be included in the summary tables of TEAEs. Pretreatment AEs are defined as AEs that start after informed consent but before the first dose of study intervention.

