## 6.1.5. Derivation of Prior or Concomitant Medications for Missing or Incomplete Dates

If both start and end dates of medications are completely missing, no imputation will be performed, and those medications will be considered both prior and concomitant medications.

If the end date is partial:

- 1. If only the day is missing
  - a. If the year and month coincide with those of the last study intervention administration date, then the end of medication will be set to the last study intervention administration date.
  - b. If the year and month do not coincide with those of the last study intervention administration date, then the missing day will be imputed as the last day of the month considering leap year and month.
- 2. If both day and month are missing
  - a. If the year coincides with that of the last study intervention administration date, then the missing month and day will be imputed as the month and day of the last study intervention administration.
  - b. If the year does not coincide with that of the last study intervention administration date, then the missing month and day will be imputed as "12" and "31," respectively.

If the start date is partial:

- 1. If only the day is missing
  - a. If the year coincides with that of the first study intervention administration date, then do the following:
  - b. If the month does not coincide with that of the first study intervention administration date, then impute the missing day as "01."
  - c. If the month coincides with that of the first study intervention administration date
    - i. If the end date is greater than the first study intervention administration date, then impute the missing day as the day of the first study intervention administration date.
    - ii. If the end date is less than or equal to the first study intervention administration date, then impute the missing day as the day of the end date of medication.
  - d. If the year and the month do not coincide with those of the first dose date, then impute the missing day as "01."
- 2. If both day and month are missing:
  - a. If the year does not coincide with that of the first study intervention administration date, then impute the missing month as "01" and missing day as "01."
  - b. If the year coincides with that of the first study intervention administration date

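### The SAP's rule for a missing AE start day in the first-dose month compares days of the month, not dates, so some AEs ending in a later month are back-dated before dosing and leave the TEAE tables

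*SAP*

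**What the plan says.** SAP 6.1.4 covers partial onset dates. Rule 1a applies when only the day is missing and carries this condition: "If the month/year of the start date is the same as those of the first study intervention administration date". The day is then "imputed as the smaller nonmissing value of (day of the first study intervention administration, day of the AE end date"). The rule does not mention the month of the AE end date.

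SAP 4.6.2 decides where the event goes:

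- "Treatment-emergent AEs are defined as any AE with a start date on or after the first dose of study intervention in the RCP".
- "Pretreatment AEs are defined as AEs that start after informed consent but before the first dose of study intervention". These go to a separate listing, and "These AEs will not be included in the summary tables of TEAEs".

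Three other rules bear on this:

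- Rule 2a of SAP 6.1.4 (day and month both missing, onset year equal to the first-dose year) starts from the first-dose date and then makes a full-date check: "If this leads to a date after the AE end date".
- SAP 6.1.5, the parallel rule for medications with a missing start day in the first-dose month, also tests full dates: "If the end date is greater than the first study intervention administration date, then impute the missing day".
- SAP 6.1.4 treats an AE with both dates completely missing as treatment-emergent.

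**The concern.** The smaller of two day numbers is the earlier of two dates only when both fall in the same month. Once an AE runs past the month-end, a low end-day number no longer means an early date. Rule 1a nevertheless lets it pull the onset back before dosing.

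The classification then depends on something irrelevant to onset, namely whether the end-day number is below the dose-day number. An AE that is ongoing at one data cut could count as a TEAE and then leave the table when its end date is entered. Compared with a full-date rule, the error can only move events out of the TEAE tables, never into them.

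Characterising safety is a stated Part A objective, and Protocol 9.4.2.1 bases AE reporting on TEAEs. With about 36 participants, any event lost from a row is visible. Part B will have its own SAP, and the rule could be carried into it.

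**Working it through.** The plan gives no figure to reproduce. The check codes rule 1a as written, codes a full-date version, and applies the SAP 4.6.2 definition to both.

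**Inputs**

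- Rule 1a as written: onset = first-dose month and year, with day = min(dose day, end day), ignoring a missing end date.
- Full-date version: onset = min(first-dose date, AE end date), ignoring a missing end date.
- TEAE if onset ≥ first-dose date (SAP 4.6.2).

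**Worked example:** first dose 20 March 2023, AE start March 2023 with the day missing.

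| AE end | Rule 1a onset | TEAE? | Full-date onset | TEAE? |
|---|---|---|---|---|
| 10 March | min(20, 10) = 10 March | No | 10 March | No |
| 25 March | min(20, 25) = 20 March | Yes | 20 March | Yes |
| 5 April | min(20, 5) = 5 March | **No** | 20 March | Yes |
| 25 April | min(20, 25) = 20 March | Yes | 20 March | Yes |
| Ongoing | 20 March | Yes | 20 March | Yes |

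Only the 5 April row differs, with onset placed 20 − 5 = 15 days before dosing.

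**How often the rule back-dates.** The condition is an AE with a missing start day in the dose month and an end date in the following month.

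- Simple model, dose day d and end day uniform on 1–30: P(end day < d) = (d − 1)/30. This is 9/30 = 30% for d = 10, 19/30 = 63% for d = 20 and 24/30 = 80% for d = 25. Averaged over d, it is 435/900 = 48.3%.
- Calendar enumeration over every first-dose day of 2023 (an illustrative year): 5,370 of 11,098 pairs = 48.4% under rule 1a, and 0 of 11,098 under the full-date version.
- With the end date in the dose month, the two versions agree in all 11,111 pairs. A full-date rule therefore changes only the cross-month cases.

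**How often a true post-dose event is lost.** Back-dating is an error of fact only if onset really was on or after dosing. Assume in addition that onset is uniform over the 30 days and independent of the end day. Then P(back-dated and onset ≥ dose) = (d − 1)/30 × (31 − d)/30.

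- d = 10: 0.30 × 0.70 = 21%
- d = 20: 0.63 × 0.37 = 23%
- d = 25: 0.80 × 0.20 = 16%
- Average over d = 1–30: 4,495/27,000 = 16.6%, or about 17%. That is 4,495/13,050 = 34% of the back-dated cases.

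**Dependence on duration.** The next shares are restricted to AEs with true onset on or after dosing that end in a later month, by assumed duration:

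| Days | 7 | 14 | 21 | 28 | 42 | 56 | 90 |
|---|---|---|---|---|---|---|---|
| Back-dated | 85% | 69% | 46% | 14% | 46% | 26% | 9% |

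These are calendar enumerations, not predictions for the trial. The matching figure from the uniform model is 4,495/27,000 ÷ 465/900 = 32%.

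**Partial stop dates.** For a stop date with only the day missing, SAP 6.1.4 says: "The missing day will be imputed as the last of the month, adjusting for the leap year". Such AEs are affected only when the stop month is shorter than the dose day, for example dose 31 March and stop April, giving onset 30 March.

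**The case against.** The best defence is that this is a drafting slip with little practical effect. Four conditions must coincide: only the start day is missing, the onset month is the dose month, the AE ends in a later month, and the end day is below the dose day. No affected AE is shown to exist. The rule takes no account of treatment arm, and the safety summaries are descriptive. All of that stands and limits the size of the point.

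One could also read day as date. The wording does not support this: the rule fills a missing day from two day values, and the section says date, or day and month, where it means those. A programmer would code the day-of-month minimum. If full dates were intended, the sentence still needs correcting.

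A reader might infer several stronger claims that the documents do not support:

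- *That about half of such AEs are wrongly excluded.* The 48% is the chance of back-dating. AEs are collected from consent (Protocol 8.3.1) and screening lasts up to 42 days, so some of these events did start before dosing. Calling all of them misfiled presupposes that uncertain onset always counts as emergent, a default SAP 6.1.4 states only when both dates are completely missing.
- *That the rule removes the longer-lasting events.* Ongoing AEs are kept, and among cross-month AEs the short ones are hit most.
- *That infusion-reaction, SAE or AESI counts will be too low.* These events are the least likely to lack a start day. Dosing is supervised with date and time recorded (Protocol 6.4). Infusion reactions that interrupt or stop treatment, and SAEs, are notified within 24 hours (Protocol 10.1 and 8.3.1), and a visit follows on Day 15 ± 2. An undercount is possible but not shown.
- *That the events vanish.* They stay in the pretreatment listing, and deaths, SAEs and AEs leading to discontinuation have their own listings (SAP 4.6.2).

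**Conclusion.** The point holds as a defect in the text of SAP 6.1.4. Rule 1a can place the onset of an AE before dosing because the AE ended early in a later month, and SAP 4.6.2 then takes it out of the TEAE tables. No other rule in the SAP corrects this, and rule 2a and SAP 6.1.5 handle their parallel cases with full dates.

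Given a missing start day in the dose month and an end date in the following month, about 48% of dose-day/end-day pairs are back-dated (uniform days). About 17% are both back-dated and truly post-dose if onset is also uniform over the month and independent of the end day. Among truly post-dose cross-month AEs, the back-dated share runs from 9% to 85% over assumed durations of 7 to 90 days. The documents do not say how many AEs will have partial dates, so the count affected is unknown and probably small. The case for change rests on the rule being wrong as written and cheap to correct, not on a demonstrated bias in the safety results.

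**What to change.** Replace rule 1a in SAP 6.1.4 with a full-date rule, for example: *When only the start day is missing and the onset month and year match those of the first dose, set the onset date to the first-dose date; where that is later than the AE end date, set it to the AE end date.* Use the same wording in the Part B SAP.

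The cost is one sentence and one line of derivation code, with no change to data collection or visits. The downside is that a few more events of uncertain onset, some of which began before dosing, may count as TEAEs.

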## 6.1.5. Derivation of Prior or Concomitant Medications for Missing or Incomplete Dates

If both start and end dates of medications are completely missing, no imputation will be performed, and those medications will be considered both prior and concomitant medications.

If the end date is partial:

- 1. If only the day is missing
  - a. If the year and month coincide with those of the last study intervention administration date, then the end of medication will be set to the last study intervention administration date.
  - b. If the year and month do not coincide with those of the last study intervention administration date, then the missing day will be imputed as the last day of the month considering leap year and month.
- 2. If both day and month are missing
  - a. If the year coincides with that of the last study intervention administration date, then the missing month and day will be imputed as the month and day of the last study intervention administration.
  - b. If the year does not coincide with that of the last study intervention administration date, then the missing month and day will be imputed as "12" and "31," respectively.

If the start date is partial:

- 1. If only the day is missing
  - a. If the year coincides with that of the first study intervention administration date, then do the following:
  - b. If the month does not coincide with that of the first study intervention administration date, then impute the missing day as "01."
  - c. If the month coincides with that of the first study intervention administration date
    - i. If the end date is greater than the first study intervention administration date, then impute the missing day as the day of the first study intervention administration date.
    - ii. If the end date is less than or equal to the first study intervention administration date, then impute the missing day as the day of the end date of medication.
  - d. If the year and the month do not coincide with those of the first dose date, then impute the missing day as "01."
- 2. If both day and month are missing:
  - a. If the year does not coincide with that of the first study intervention administration date, then impute the missing month as "01" and missing day as "01."
  - b. If the year coincides with that of the first study intervention administration date
    - i. If the end date is greater than the first study intervention administration date, then impute the missing day and month as those of the first study intervention administration.

c. If the start date is completely missing, the missing start date will be set as the earlier of the first study intervention administration date and the end of the medication date.

For meningococcal vaccination, the missing end date will not be imputed.

